1.2. Study Design

This is a Phase 2, multicenter, open label study evaluating the safety, tolerability, PK, PD, and effect on COAs of AL001 administered intravenously (60 mg/kg, q4w) in asymptomatic and symptomatic carriers of loss-of-function GRN mutations causative of FTD and in symptomatic carriers of C9orf72 hexanucleotide repeat expansion mutations causative of FTD. This study has two parts: A phase 2 open-label treatment period (Part 1), followed by an optional open-label extension (OLE) period (Part 2).

Part 1 is a 96-week evaluation of the safety, tolerability, PK, PD, and clinical effect of AL001 administered intravenously (60 mg/kg, every 4 weeks [q4w]), for a total of 25 doses (96-week dosing period), in asymptomatic and symptomatic carriers of loss-of-function GRN mutations causative of FTD, and in symptomatic carriers of C9orf72 hexanucleotide repeat expansion mutations causative of FTD.

Part 2 is an optional OLE for eligible participants who have completed the 96-week Part 1 treatment period. The OLE period will evaluate the long-term safety and tolerability of AL001 administered at the same dose and regimen as Part 1 (60 mg/kg, q4w), for up to a total of 25 doses (96-week optional OLE period).

Figure 1-1 Overview of Study Schema

Abbreviations: COA, clinical outcome assessment; CSF, cerebrospinal fluid; *GRN*, granulin; IV, intravenous; MRI, magnetic resonance imaging; PD, pharmacodynamic; q4w, every 4 weeks.

2. General Statistical Considerations

All data collected from enrolled participants, excluding screen failures, will be presented in data listings. Data from participants excluded from an analysis set will be presented in the data listings but not included in the calculation of summary statistics for the corresponding analysis set.

Data from Part 1 and Part 2 will be combined and will not be analyzed separately.

For categorical variables, frequencies and percentages will be presented. Continuous variables will be summarized using descriptive statistics (number of participants, mean, standard deviation [SD], median, minimum, maximum, and 90% or 95% confidence interval [CI] where applicable). All summaries will be presented by the three cohorts [asymptomatic FTD-*GRN* (aFTD-GRN), symptomatic FTD-*GRN* (FTD-*GRN*), symptomatic FTD-*C9orf72* (FTD-*C9orf72*)] and All Participants.

Baseline will be defined as the last non-missing assessment, including repeated and unscheduled measurements, prior to the start of first study drug administration.

Due to the high rate of participant attrition over the study duration and small FTD cohort sizes, time points beyond week 49 will not be included in the cohort level summary of the figures.

All CIs will be 2-sided and performed using a 5% significance level except for PK parameters for which, 90% CI and geometric mean will be used. All p-values will be presented to 3 decimal places and values less than 0.001 or greater than 0.999 will be presented as <0.001 and >0.999, respectively. As the objectives of the study are exploratory in nature no adjustments for multiplicity will be made.

No formal significance testing will be performed.

Analysis visit windows will be applied for COA and Biomarker analysis. A detailed explanation about the analysis visit windows will be described in the specific section of each analysis,

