8.2. Analysis Populations

Part 1 (Treatment Period)

The following analysis sets will be used in the statistical analyses:

Enrolled Population: The enrolled population will consist of all participants who signed the ICF.

Safety Analysis Population: The safety analysis population will consist of all participants who received at least 1 dose of AL001. The safety analysis population will be used for safety summaries.

PK Analysis Population: The PK analysis population will include all participants in the safety population who had adequate assessments for determination of at least 1 PK parameter. The PK analysis population will be used for PK summaries.

Full Analysis Population: The full analysis population will include all participants in the safety analysis population who had both a baseline and at least 1 post-dose assessment. The full analysis population will be used for all PD and PD biomarker summaries.

Part 2 (Option OLE)

Part 2 analyses will include all participants who received at least 1 dose administration in Part 2.

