8.4. Statistical Analysis Methodology

The main statistical analysis will be performed on Part 1. The statistical analysis will be performed using SAS software Version 9.4 or later (SAS Institute Inc., Cary, North Carolina, USA). The statistical methods for this study will be described in a detailed Statistical Analysis Plan (SAP), which will be finalized before locking of the database. Changes from analyses planned in this protocol will be documented in the SAP. Any deviations from the planned analysis as described in the SAP will be justified and recorded in the final clinical study report (CSR).

For categorical variables, frequencies and percentages will be presented. Continuous variables will be summarized using descriptive statistics (number of participants, mean, standard deviation [SD], median, minimum, maximum, and 95% confidence interval [CI] where applicable). All summaries will be presented by combined participant status and dementia type at baseline (aFTD-*GRN*, FTD-*GRN* [bvFTD and PPA], FTD-*C9orf72* [bvFTD and PPA], and All Patients).

Part 1 (Treatment Period)

In Part 1, data collected for participants who failed screening and were not enrolled will not be presented in any summaries or data listings. All other data will be listed in data listings. Baseline will be defined as the last non-missing assessment, including repeated and unscheduled measurements, prior to the start of first study drug administration.

In Part 1, all CIs will be 2-sided and performed using a 5% significance level, except for PK parameters, for which 90% CI and geometric mean will be used. As the objectives of the study are exploratory in nature no adjustments for multiplicity will be made.

No formal significance testing will be performed.

Part 2 (OLE)

For Part 2, no formal statistical testing will be performed. Descriptive statistics will be presented for Part 2 separately from Part 1. The purpose of the OLE is to collect continued long-term (up to 96 weeks) safety and tolerability data from participants who have completed Part 1 of the study. As the objectives of the OLE are exploratory in nature no adjustments for multiplicity will be made.

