Primary	The primary objective of the OLE period of the study is to assess the long-term safety and tolerability of AL001 in participants who have completed 96 weeks of treatment on Part 1 of the study.	
 • Incidence, nature, and severity of AEs and SAEs • Incidence of treatment discontinuations and study discontinuations due to AEs • Physical examination abnormalities • Neurological examination abnormalities • Changes in vital signs from baseline over time • Changes in ECGs from baseline over time • MRI abnormalities after dosing relative to baseline • Changes in clinical laboratory tests from baseline over time • Sheehan-STS

		
 • Incidence of ADAs to AL001
Exploratory	
COAs, correlative assessments (e.g., biomarker) and other efficacy assessments conducted during the OLE are considered exploratory. The exploratory objectives of the OLE period of the study are to assess the long-term effect of AL001 in participants who have completed 96 weeks of treatment on Part 1 of the study on the following:
 
 • PK • Longitudinal plasma and CSF PGRN concentration levels • Longitudinal blood, plasma, and CSF concentration levels of exploratory biomarkers of neurodegeneration, lysosomal function, and glial activity • Magnetic resonance imaging (MRI) measures to evaluate changes in the brain 	
Serum concentration of AL001 at specified time points
 
 • AL001 PK parameters (if data permit) 
 ◦ C_{max} ◦ C_{trough} ◦ AUC_{ss} • The overall change from baseline in PGRN in plasma • The overall change from baseline in exploratory biomarkers of neurodegeneration, lysosomal function, and glial activity in blood, plasma, and CSF • Global and regional brain MRI atrophy measures
	
 • Correlations among exploratory fluid PD biomarkers, imaging PD measures, and clinical outcome assessments (COAs) 	
 • Correlations among exploratory fluid biomarkers, imaging measures, and COAs
	
 • Clinical progression as measured by COAs 	
The overall change from baseline on the scores of the instruments in the COAs
 
 • CDR® plus NACC FTLD • FRS • CGI-I • CGI-S • CTT Part 2 • RBANS

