Adverse Events will be coded by SOC and PT according to MedDRA, version to be delineated in the CSR.

All summary tables will include counts and frequency of participants and number of events. Subject incidence rate of AEs will be summarized by SOC and PT and for PT only. The summary will be provided separately by overall descending incidence rate and then by alphabetical order. A separate summary will be provided by alphabetical order for SOC and PT. A participant with 2 or more occurrences for the same AE, the subject will be counted only once in that level using the worst severity (for the severity table) or the most related (for the relationship to study drug table). Percentages will be based upon the number of participants in the Safety population.

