6.4. Triplicate 12-Lead Electrocardiograms

Triplicate 12-lead ECGs will be obtained after the participant has been in the supine position for ≥ 5 minutes. ECG measurements will be collected at the timepoints identified in [Appendix 14.1](#), [Appendix 14.2](#), [Appendix 14.4](#) and [Appendix 14.5](#).

All ECGs will be analyzed from a clinical safety basis (without intensive QT analysis). The clinical significance of ECG changes will be determined by the investigator after review of the ECG report in relation to the participant's medical history, PE, and concomitant medications and documented on the eCRF.

For summaries of quantitative triplicate 12-lead ECG parameters, the average of the triplicate 12-lead ECG measurements will be used for the determination of baseline and calculation of summary statistics.

For interpretation of triplicate 12-lead ECGs, baseline will be defined as the best case of the last non-missing triplicate measurements (including repeated and unscheduled measurements) before the start of first study drug administration. For calculation of post-dose summary statistics, the worst case of the non-missing triplicate measurements will be used. The order of interpretation

for 12-lead ECGs (best to worst case): Normal; Abnormal, Not Clinically Significant; Abnormal, Clinically Significant. Interpretations of Indeterminate, Not Evaluable, or Unknown will not be considered when determining the worst or best case.

Actual values and changes from baseline for quantitative ECG results will be summarized at each time point using descriptive statistics.

Shift from baseline in ECG interpretation and clinical significance will be summarized by visit using the frequency count and percentage of participants in each category.

In addition, the number (percentage) of subjects with at least 1 post-baseline abnormal ECG result in corrected QT interval calculated using Fridericia's formula (QTcF) interval, PR, QRS or HR will be summarized. Clinically abnormal ECG results will be categorized as follows:

Absolute QTcF interval prolongation:

- QTcF interval >450 msec
- QTcF interval >480 msec
- QTcF interval >500 msec

Change from baseline in QTcF interval:

- QTcF interval increases from baseline >30 msec
- QTcF interval increases from baseline >60 msec
- PR < 120 msec
- PR > 200 msec
- QRS < 60 msec
- QRS > 100 msec
- HR < 60 bpm
- HR > 100 bpm

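### The SAP pools Part 1 with the extension and bars separate analysis, against the protocol, so adverse-event incidence is tabulated for neither part's primary objective

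*SAP*

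**What the plan says.** The SAP's general rule (Section 2) is "Data from Part 1 and Part 2 will be combined and will not be analyzed separately". Protocol 8.4 says of the extension: "Descriptive statistics will be presented for Part 2 separately from Part 1". Protocol 8.2 sets its denominator: "Part 2 analyses will include all participants who received at least 1 dose administration in Part 2". SAP 2.3 defines Enrolled, Safety, PK and Full Analysis populations and no Part 2 population.

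Protocol 8.4 also says: "Changes from analyses planned in this protocol will be documented in the SAP". SAP Section 12 lists the dropped examination summaries, the Week 49 limit on figures, apolipoprotein B100, Sortilin and some MRI analyses. It does not list the pooling.

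SAP 1.1 still carries two primary objectives. Table 1 concerns safety over 96 weeks. Table 2 begins: "The primary objective of the OLE period of the study is to assess the long-term safety and tolerability of AL001", and restricts this to people who completed Part 1. Each table lists the incidence of AEs and SAEs first among its endpoints.

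For AE tables, SAP 6.1 says: "Percentages will be based upon the number of participants in the Safety population", and "A participant with 2 or more occurrences for the same AE, the subject will be counted only once in that level". SAP 6.4 adds a table of "the number (percentage) of subjects with at least 1 post-baseline abnormal ECG result".

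**The concern.** The two documents cannot both be followed. A percentage with all treated participants as denominator, counted from first dose to the end of all follow-up, answers neither question. It is not a 96-week incidence, because some people contribute a second treatment period. It is not an extension incidence, because people who never entered Part 2 are in the denominator. An event that occurs in Part 1 and again in Part 2 adds nothing to the percentage. The figure also has no fixed time frame: it moves with attrition, uptake into Part 2 and how completely people are followed after stopping drug.

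The problem is confined to summaries not made by visit: the AE, SAE and discontinuation tables and the ECG outlier table. Laboratory, vital-sign, quantitative ECG, Sheehan-STS and anti-drug-antibody summaries by visit still separate the parts and are not criticised.

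**Working it through.** **The plan's own figure.** Protocol 8.1 and SAP 2.1 give the chance of at least one finding among 40 participants in Part 1. With 1 − (1 − p)^40 at p = 0.1%, 1%, 5% and 10%, I get 3.92%, 33.10%, 87.15% and 98.52%, against the stated 3.9%, 33.1%, 87.1% and 98.5%. They reproduce. They refer to 40 people in Part 1 only, a frame that no planned AE table uses.

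**Length of the pooled window.** The last Part 2 dose is at Week 197, which is 196 weeks after the first dose. Adding the 10-week safety visit gives 206 weeks.

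**Denominator effect.** Suppose 20 of 40 enter Part 2 and four people have an event, all in Part 2. The pooled table shows 4/40 = 10%. On the protocol's Part 2 denominator it is 4/20 = 20%.

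**Time-frame effect (illustration).** The documents give no AE, attrition or uptake rates; the SAP says only that attrition is high. Assumptions:

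- AE risk of 30% over 96 weeks, constant hazard, AEs do not cause stopping;
- Part 1 attrition a of 30% or 50%, with the same dropout rate in the extension;
- 80% of Part 1 completers enter Part 2, which runs from Week 100 to Week 196 after first dose;
- the 10-week follow-up is not added.

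Hazards: λ = −ln(0.7)/96 = 0.00372 per week; μ = −ln(1 − a)/96 = 0.00372 (a = 30%) or 0.00722 (a = 50%).

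Part 1 crude percentage if follow-up ends at dropout (case A): P1 = λ/(λ+μ) × [1 − exp(−96(λ+μ))].

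- a = 30%: 0.500 × (1 − 0.49) = 0.255
- a = 50%: 0.340 × (1 − 0.35) = 0.221

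Amount added by the extension: (1 − a) × 0.8 × 0.7 × [g + (1 − g) × P1]. Here g = 1 − 0.7^(4/96) = 0.015 is the risk in the four weeks between parts, and the risk within the extension equals P1 because the rates are the same.

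- a = 30%: 0.392 × 0.266 = 0.104
- a = 50%: 0.280 × 0.232 = 0.065

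Case B follows everyone to Week 96 whether or not they stop drug, as protocol 3.3.1 intends, so Part 1 is 0.300.

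| Case | Attrition | Part 1 | Pooled |
|---|---|---|---|
| A | 30% | 26% | 36% |
| A | 50% | 22% | 29% |
| B | 30% | 30% | 40% |
| B | 50% | 30% | 37% |

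Under A, varying uptake from 50% to 100%, with extension dropout either the same or none, gives pooled values of 32–41% at 30% attrition and 26–33% at 50%.

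Entrants to Part 2: 40 × 0.7 × 0.8 = 22.4, or 40 × 0.5 × 0.8 = 16.0.

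**Events hidden by once-only counting.** Among entrants with a Part 2 event, the share who already had that event before the first Part 2 dose is 1 − 0.7^(100/96) = 31%, if events are independent. It is larger if susceptibility varies between people.

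**Lower risk.** At 10% risk, case B gives pooled 14.5% and 12.8% against 10%. These gaps are 0.045 × 40 = 1.8 and 0.028 × 40 = 1.1 people, and the hidden share falls to about 10%. At 5% risk the gap is under one person.

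**The case against.** The pooling is stated openly in SAP Section 2, and the protocol does not say where in the SAP a change must be recorded. That is true. What is missing is any identification of it as a change, or a reason. The Week 49 limit on figures appears in both Section 2 and Section 12, so the SAP's own practice is to repeat such changes there.

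Part of the 29–40% spread comes from attrition, not pooling. Under case A the Part 1 crude figure is itself below 30%, and pooling always raises it. This stands: like for like, pooling adds about 7 to 10 points, and separate tables would not remove the attrition effect. The proposed Part 1 window is not exactly 96 weeks either, since it ends near Week 101 for entrants and at Week 107 for other completers.

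The 30% risk suits common events or any AE. For rarer events the gap is one or two people or fewer, as shown. The denominator problem for Part 2 remains at any risk.

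The study is single-arm and descriptive, no decision rule uses the percentage, event counts are tabulated, all safety data are listed, and dosing runs unbroken from Week 97 to Week 101. These points limit the harm and support keeping a combined table. They do not supply the incidence by part, which a reader would have to rebuild by hand; the SAP itself classes analyses made after database lock as post hoc.

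**Conclusion.** The concern holds and must be fixed. The contradiction with protocol 8.2 and 8.4 is explicit and needs no assumption, and the change is neither listed nor explained. As written, the first-listed primary endpoint of each part has no planned table. The numerical size is illustrative only: about 7 to 10 percentage points above the Part 1 figure at a 30% risk, and 3 to 4 points at 10% in case B, under a constant hazard and 80% uptake. Confidence in the textual finding is high. The true size cannot be known from these documents.

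**What to change.** In SAP Sections 2, 2.3 and 6:

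1. Delete the pooling sentence and add a Part 2 population: participants with at least one dose in Part 2.
2. Produce the AE, SAE and AE-discontinuation tables and the ECG outlier table three ways, counting each participant once within each part:
   - Part 1: from first dose to the earlier of first Part 2 dose or the end of Part 1 follow-up, including the 10-week safety visit and any visits continued after stopping drug; denominator all treated.
   - Part 2: onset or worsening from first Part 2 dose; denominator those dosed in Part 2.
   - Combined: as a supplement.
3. List any remaining departure from protocol 8.2 or 8.4 in SAP Section 12, with its reason.

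Optional: add rates per participant-year from the exposure duration in SAP 5.3. Separately, SAP Table 1 mentions evaluation by dose, for example by tertiles, and no SAP section carries it out. If it is done, use exposure accrued up to the event or rates by time interval: on a single regimen, final cumulative dose largely tracks time on drug and is itself affected by AEs that stop treatment.

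The cost is SAP wording, one population and extra table shells from data already collected. No protocol amendment is needed, because the change returns the SAP to its protocol. The drawback is small extension cells (16 to 22 people over three cohorts in the illustration). Part 2 entrants are also selected completers, so their percentages are descriptive and not comparable with Part 1.
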